7.2 Safety Analysis Set

For each part of the study, the safety analysis set will be the same as the FAS. All other analysis sets will be a subset of FAS.

7.3 DLT Analysis Set

All subjects who are DLT-evaluable are included in this analysis set as defined in [section 8.1.1.2](#)

7.4 Pharmacokinetic Analysis Set

All subjects who received any blinatumomab and had at least one PK sample collected will be included in the PK analysis set. These subjects will be evaluated for PK unless significant protocol deviations affect the data analysis or if key dosing, dosing interruption, or sampling information is missing.

7.5 Pharmacodynamic Analysis Set

All subjects who had cytokine and/or lymphocyte subset samples collected at baseline or any time during the study will be included in the PD analysis set.

8. Interim Analysis and Early Stopping Guidelines

8.1 Interim Analysis

Safety data will be reviewed on an ongoing basis using an as-is database snapshot. Amgen, in consultation with the site investigator, will review in DLRT meetings all available accumulating data by multiple subject cohort before making dosing decisions. Adverse events and DLTs observed in all subjects will be evaluated continually and will be fully integrated into all DLRT meetings and considered in all enrollment and dosing decisions.

DLRT meetings will be held to review data, monitor safety, and make dosing decisions.

8.1.1 Dose-cohort Study Escalation and Stopping Rules

8.1.1.1 Dose Level Review Team

The DLRT meeting will be held to review data, monitor safety, and make decisions on dose escalation/change, or changes in pre-medication. The DLRT will be composed of the investigators or designees, and the following Amgen representatives: medical monitor, global safety officer or designee, clinical study manager, biostatistician, PK scientist (optional), and other functional area representatives as appropriate. A quorum as defined below must be in attendance for the DLRT. The quorum is defined as > 50% of the participating investigators (defined as the number of investigators that had subjects enrolled on the cohort for that DLRT meeting) or their qualified designee (ie, sub-investigator or research nurse or study coordinator possessing written documentation [eg, e-mail] of the investigator's vote), as well as > 50% of Amgen representatives listed above. The medical monitor or designee must attend for the quorum to be reached. The DLRT will be rescheduled if a quorum is not reached.

The following members are responsible for DLRT decisions: investigators, Amgen medical monitor, and global safety officer or designee.

The following decisions may be made by the DLRT:

- dose escalation/de-escalation decisions
- changes in dosing frequency
- expansion of a cohort
- continuation, delay or termination of dosing

All available study data, including demographics, investigational product administration, medical history, concomitant medications, adverse events, vital signs, laboratory data, and PK/PD information will be reviewed. In addition to DLTs, all \geq grade 3 toxicities not

meeting DLT criteria will be reviewed and may be considered in DLRT decisions. Source data and queries do not need to be resolved before the DLRT. Continuous toxicity monitoring for early termination of the trial in Cycle 1/Period 2 will be performed. All adverse events that occur the DLT window will be reviewed and may be considered in DLRT decisions.

8.1.1.2 Dose Limiting Toxicity Rules

Cycle 1/Period 1

The DLT evaluation period includes the entire week 4 (7 days) which is the week that blinatumomab is administered SC during Cycle 1/Period 1 of the study. To be evaluable subjects need to fulfill the criteria described in [section 6](#).

If ≤ 1 of the 6 evaluable subjects in a dose SC cohort experience a DLT during the SC administration, then the dose will be determined to be tolerable and the next dose-cohort level will be initiated in a new dose-cohort of subjects after review by the DLRT.

If ≥ 2 subjects of the 6 evaluable subjects in a SC dose cohort experience a DLT during SC administration then dosing will stop for individual subjects who experience a DLT, a DLRT meeting will be conducted, and further steps will be determined.

Additionally, the DLRT will meet:

- once dose-cohort 1 has completed subcutaneous dosing
- once dose-cohorts 2 and 3 have completed subcutaneous dosing
- once any additional cohorts complete dosing if additional dose-cohorts are tested to determine the MTD in Cycle 1/Period 1

Cycle 1/Period 2

For subjects who receive optional Cycle 2 (cIV dosing period) after Cycle 1/Period 2 (SC dosing period), the DLT evaluation period includes the entire duration of SC administration in Cycle 1 and 16 days following the last SC dose (56 days in total) or until the start of optional Cycle 2, whichever is longer, up to 30 days after the last SC dose of Cycle 1. For subjects who do not receive optional Cycle 2, the DLT evaluation period includes the entire duration of SC administration and 30 days following the last SC dose (70 days in total). Continuous monitoring for early termination of the trial will be performed by DLRT (refer to [Section 3.1.3](#) and [Section 8.1.1](#)).

9. Data Screening and Acceptance

9.1 General Principles

The objective of the data screening is to assess the quantity, quality, and statistical characteristics of the data relative to the requirements of the planned analyses.

9.2 Data Handling and Electronic Transfer of Data

Amgen's Clinical Data Management (CDM) department will provide all data to be used in the planned analyses. The database will be subject to edit checks outlined in the Clinical Data Management Plan (DMP). See details of this section in the DMP.

9.3 Handling of Missing and Incomplete Data

The following imputation of missing values will be done:

- Incomplete adverse event and concomitant medication dates will be imputed as per [Appendix A](#)
- No data imputation for PK and biomarker data.

9.4 Detection of Bias

Lack of protocol compliance and the potential for biased statistical analyses will be examined by assessing the incidence of important protocol deviations. The clinical study team will identify and document the criteria for important protocol deviations following Amgen SOP.

9.5 Outliers

Details of detecting outliers can be found in the DMP or other data management document. In addition, outliers may be identified via the use of descriptive statistics. All confirmed outlier data will be included in the analyses presented in this statistical analysis plan unless there is sufficient scientific justification to exclude them.

9.6 Distributional Characteristics

Where appropriate, the assumptions underlying the proposed statistical methodologies will be assessed. Data distribution will be explored, if required, data transformations or alternative non-parametric methods of analyses will be utilized.

9.7 Validation of Statistical Analyses

Programs will be developed and maintained and output will be verified in accordance with current risk-based quality control procedures.

Tables, figures, and listings will be produced with validated standard macro programs where standard macros can produce the specified outputs.

The production environment for statistical analyses consists of Amgen-supported versions of statistical analysis software; for example, the SAS System version 9.4.

10. Statistical Methods of Analysis

10.1 General Principles

Descriptive statistics will be provided for selected demographics, safety, immunogenicity, PK, PD, and biomarker data. Descriptive statistics on continuous measurements will include means, medians, standard deviations, and ranges, while categorical data will be summarized using frequency counts and percentages. Data will be summarized by dose cohort and by time as appropriate. Graphical summaries of the data may also be presented. When data are summarized by time, the scheduled time points listed in the protocol will be used). For statistical analyses comparing change from baseline, only subjects with both baseline and at least one post-baseline assessment will be included. When assessing minimum/maximum increases or decreases over the study, all assessments, including unscheduled assessments will be used.

The final analysis will be triggered when target enrolment is complete, and all subjects complete the study or withdraw from the study. The data will be analyzed once they have been entered, cleaned, and locked.

10.2 Subject Accountability

The number and percent of subjects who were screened, enrolled, received at least one dose of blinatumomab, completed investigational product, discontinued from investigational product (including reasons for discontinuing), completed study, discontinued the study (including reasons for discontinuing) will be summarized overall and by dose cohort.

Key study dates for the first subject enrolled, last subject enrolled, and last subject's end of study will be presented.

A subject listing and summary noting inclusion in each analysis subset will be provided for all subjects enrolled. A subject listing noting, reason for discontinuation of treatment, and reason for discontinuing the study will be provided. A list of subjects screened but not enrolled (screen failures) will be provided.

10.3 Important Protocol Deviations

Important Protocol Deviations (IPDs) categories are defined by the study team before the first subject's visit and updated during the IPD reviews throughout the study prior to database lock. If a snapshot is being taken during the study rather than a database lock at the end of the study, categories should be updated during the IPD reviews throughout the study prior to database lock. These definitions of IPD categories, sub-category codes, and descriptions will be used during the course of the study. Eligibility deviations are defined in the protocol. The final IPD list is used to produce the list of subjects with IPDs. In addition, a separate listing of all inclusion and exclusion deviations will be provided.

10.4 Demographic and Baseline Characteristics

Demographic (ie, age, age groups [18-64, 65-74, 75-84 and \geq 85], sex, race, ethnicity) and baseline characteristics will be summarized by dose cohort and overall using descriptive statistics. If multiple races have been reported for a subject, the subject will be categorized as multiple race as well as by the combination of race.

The baseline characteristics to be summarized include:

- Height
- Weight
- NHL Subtype: FL, Marginal zone lymphoma, Lymphoplasmocytic lymphoma, MCL and Small lymphocytic lymphoma
- Line of Previous Therapies: 1st line, 2nd line, 3rd line, 4th line and Other

A listing of Non-Hodgkins Lymphoma Medical History will be provided.

10.5 Safety Analyses

Unless otherwise specified, statistical analyses on safety endpoints will be done using subjects from the full analysis set, which includes subjects that are enrolled and received at least 1 dose of blinatumomab.

10.5.1 Adverse Events

The Medical Dictionary for Regulatory Activities (MedDRA) version 19.0 or later will be used to code all adverse events to a system organ class and a preferred term.

The severity of each adverse event will be graded using CTCAE version 4.0 criteria. Subject incidence of treatment emergent events and treatment related treatment emergent events will further be summarized by worst severity grade.

Subject incidence of all treatment emergent, serious treatment emergent, treatment related, serious treatment related, those leading to withdrawal of investigational product or other protocol-required therapies, and fatal adverse events will further be tabulated by system organ class and preferred term for each dose cohort in descending order of frequency. The above adverse event tables will include disease related events and will not be created if two or fewer subjects in the study experience the adverse event. Similar summaries will be repeated for EOIs. Time to onset and duration of selected EOIs (infection and neurologic events) may also be summarized.

Subject incidence of disease related events and fatal disease related events will be tabulated by system organ class and preferred term for each dose cohort. All DREs and fatal DREs would be tabulated by system organ class and preferred term separately.

DREs should be included with AEs in any submission datasets, integrated summaries and in CTD reporting.

Tables with AEs as above will be produced for period 1 for SC and cIV dosing separately. Listings of any on-study deaths, including early withdrawals due to adverse events will be provided should they occur.

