#### 10.4.3.1 Adverse Events

Subject incidence of all treatment-emergent adverse events will be tabulated by system organ class and preferred term. The number and percentage of subjects reporting adverse events will be evaluated overall and by dose level and will also be tabulated by relationship to study drug.

Tables of fatal adverse events, serious adverse events, adverse events leading to withdrawal from investigational product or other protocol-required therapies, and significant treatment-emergent adverse events will also be provided.

Subject incidence of disease related events and fatal disease related events will be tabulated by system organ class and preferred term.

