4.1 Study Endpoints

4.1.1 Primary Endpoint

- Subject grade, incidence, and severity of dose limiting toxicities (DLTs) and adverse events

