10.8 Pharmacodynamic Analysis

Time profiles of pharmacodynamic markers (eg, T-cell, B-cell, cytokines) may be provided if data are sufficient. Mean (SD) peak (eg, cytokine) or trough concentrations (eg, B-cells) of pharmacodynamic markers will be summarized with descriptive statistics by dose level, cohort and route of administration. Time to reach peak or trough concentrations of pharmacodynamic markers may be summarized by dose, cohort and route of administration.

11. Changes From Protocol-specified Analyses

There are no changes to the protocol-specified analyses.

12. Literature Citations / References

13. Prioritization of Analyses

There is no prioritization of analyses.

14. Data Not Covered by This Plan

Exploratory data not included in this plan may be analyzed at a later date or may be analyzed by a different Amgen Department.

15. Appendices

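### The SAP withholds adverse event tables when two or fewer subjects in the study are affected; the protocol sets no such minimum, and the change is not declared

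*SAP*

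**What the plan says.** SAP 10.5.1 sets out the incidence tables by system organ class and preferred term: "Subject incidence of all treatment emergent, serious treatment emergent, treatment related, serious treatment related, those leading to withdrawal of investigational product" (or of other required therapies), and fatal events. The next sentence says that these tables will include disease related events and that they "will not be created if two or fewer subjects in the study experience the adverse event". It is followed by "Similar summaries will be repeated for EOIs", which does not restate the threshold.

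Protocol 10.4.3.1 reads differently. It says "Subject incidence of all treatment-emergent adverse events will be tabulated by system organ class and preferred term". It then commits to "Tables of fatal adverse events, serious adverse events, adverse events leading to withdrawal from investigational product" (or other required therapies), and adds that tables of "significant treatment-emergent adverse events will also be provided". None of these commitments depends on a count.

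SAP 4.1.1 gives the primary endpoint as "Subject grade, incidence, and severity of dose limiting toxicities (DLTs) and adverse events". SAP Section 11 states: "There are no changes to the protocol-specified analyses".

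**The concern.** Three statements do not fit together: an unconditional promise of tables in the protocol, a condition on those tables in the SAP, and a SAP declaration that nothing has changed. The condition falls on primary endpoint reporting in a first-in-human study of the SC route, where much of the safety information lies in small numbers of serious events.

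The SAP also applies a stricter test to clinical events than to laboratory values. Under SAP 10.5.2.1, a laboratory parameter enters the toxicity summary once a single subject reaches grade 3 or higher, and a listing supports it. A serious or fatal clinical event needs three subjects.

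At stake is the final report. A non-fatal serious event that did not lead to withdrawal could lose its promised table, with no listing named in the SAP to take its place.

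**Working it through.** **1. Does other reporting fill the gap?**

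- Deaths and early withdrawals due to adverse events are listed whenever they occur (SAP 10.5.1). This covers two of the affected table types as individual records.
- DLTs have their own listing and summary (SAP 10.5.1.1), outside the threshold but for Period 1 only. Protocol 6.2.1.2.3 also excludes from DLT status grade 3 fever or infection, and grade 3 neurologic events and grade 3 or lower CRS or tumor lysis syndrome that settle to grade 1 or less within 7 days. A serious event of these kinds would not appear in the DLT listing.
- SAP Appendix F gives adverse event listings by cohort, but for the dose review meetings rather than the final analysis.
- Protocol 10.4.1 says in general terms that individual data will be listed. The SAP does not turn this into a named listing of serious adverse events.

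The remaining gap is non-fatal serious and serious related events without withdrawal.

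**2. How large is the threshold?**

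The documents give no figure for this rule. As a check on the binomial method, the SAP 3.2 figures for 6 subjects reproduce. At a true DLT rate of 10%, P(X ≤ 1) = 0.886 and P(X ≥ 2) = 0.114 (stated 89% and 11%). At 30% they are 0.420 and 0.580 (stated 42% and 58%).

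Inputs for the rule: about 54 subjects enrolled, giving 30 + 15 = 45 evaluable (SAP 3.2). The tables use the Full Analysis Set, meaning all treated subjects, so 54 is the main case and 45 a sensitivity case. The highest untabulated proportion is 2/54 = 3.7% (Clopper-Pearson 95% CI 0.5% to 12.7%), or 2/45 = 4.4%.

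**3. How often would an event occur and still go untabulated?**

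With X ~ Binomial(N, p), an event occurs but is withheld when X is 1 or 2:

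P(1 ≤ X ≤ 2) = N·p·(1−p)^(N−1) + [N(N−1)/2]·p²·(1−p)^(N−2)

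For N = 54 and p = 0.02, this is 0.370 + 0.200 = 0.570. Adding P(X = 0) = 0.98^54 = 0.336 gives P(X ≤ 2) = 0.906.

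The documents state no event rates, so the rates below are assumptions shown as a range.

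| Assumed true rate | N = 54: 1 or 2 affected | N = 54: 2 or fewer | N = 45: 1 or 2 affected | N = 45: 2 or fewer |
|---|---|---|---|---|
| 1% | 40% | 98% | 35% | 99% |
| 2% | 57% | 91% | 54% | 94% |
| 3% | 59% | 78% | 59% | 85% |
| 5% | 43% | 49% | 51% | 61% |
| 10% | 8% | 8% | 15% | 16% |

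At a 20% rate the chance of two or fewer is 0.06% (N = 54) or 0.3% (N = 45).

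**4. What does the rule act on?**

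The subject of the SAP sentence is a table, but its condition refers to a single adverse event. If it works by table, the rates above apply to whole categories, such as any fatal event. If it works by preferred term, they apply to each term, and rare terms drop out even of large tables. Either reading departs from the protocol; the SAP does not say which is meant.

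**The case against.** The strongest reply is that little is lost in practice. Read by table, the table of all treatment-emergent events will almost certainly exist, and it counts serious and fatal treatment-emergent events under their preferred terms; only the separate breakdown goes. The serious event table disappears only if two or fewer of about 54 subjects have any serious event: 8% at an assumed 10% rate and 0.06% at 20%. A table of one or two subjects holds little that a listing would not, and the study is descriptive, with no formal hypothesis test. Most of this stands and limits the size of the point. It does not remove the conflict with the protocol or supply the missing serious event listing.

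Some stronger readings are tempting, but the documents do not support them:

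- *Two affected subjects could be 2/6 = 33% of a cohort (exact 95% CI 4% to 78%), the count that triggers dose review.* The threshold is study-wide, so this needs both subjects in one cohort and none elsewhere. The dose review count concerns DLTs, which are reported separately. The review team also sees cohort listings and considers grade 3 or higher toxicities that are not DLTs (SAP 8.1.1.1 and Appendix F).
- *2 of 30 in the Period 1 SC tables could go untabulated.* This assumes that the count is redone for each sub-table, which the SAP does not say.
- *Event-of-interest tables promised by the protocol are removed.* The protocol does not name them; its nearest item is significant treatment-emergent events. The threshold reaches the event-of-interest summaries only by inference.
- *Rare events go unreported.* What is lost is tabulation, not all reporting.

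**Conclusion.** The point holds in a limited form. SAP 10.5.1 puts a condition on tables that the protocol promises without one, for part of the primary endpoint, and SAP Section 11 does not declare it. The effect falls on rare categories, or on rare terms if the rule works by row. At assumed true rates of 1% to 5%, an event would occur and go untabulated with probability of about 40% to 59% for 54 subjects, and 35% to 59% for 45. At 10% this falls to 8% and 15%. These figures assume independent subjects with a common rate, all 54 enrolled subjects treated, and a study-wide count as written.

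The consequence that matters is narrow: non-fatal serious and serious related events without withdrawal can lose their table, with only a generic listing commitment in the protocol behind them. Endpoint definition, data collection and dosing decisions are unaffected. It is a reporting fault that is cheap to correct.

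**What to change.** In SAP 10.5.1:

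- Remove the threshold for the fatal, serious, serious related and withdrawal tables, and for the event-of-interest summaries if it is meant to apply there.
- Add a named listing of all serious adverse events.
- If a threshold is kept for any other table, state whether it works by table or by preferred term, and whether the count is redone for the separate Period 1 SC and cIV tables. Declare it in SAP Section 11.

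The cost is about one amended SAP sentence, one listing and a few short tables. Data collection and study conduct do not change.

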**Optional Cycle 2 for Period 1:** A subject may receive a second cycle of blinatumomab if, in the investigator's opinion, the subject derives benefit from treatment. The optional cycle 2 of blinatumomab will be dosed at 9  $\mu\text{g}/\text{day}$  cIV for 7 days for days 1 through day 7, next the dose will be escalated (dose-step) to 28  $\mu\text{g}/\text{day}$  cIV for 7 days starting on day 8 through day 14, and then advanced to 112  $\mu\text{g}/\text{day}$  cIV for 28 days starting on day 15 through day 42.

**A treatment-free interval of 14 days will be observed after the completion of the first cycle of blinatumomab before starting the second cycle.**

**Optional Cycle 2 for Period 2:** A subject may receive a second cycle of blinatumomab administered SC if the subject derived clinical benefit (demonstrated on staging scans) from Cycle 1/Period 2 treatment.

If no clinical benefit occurred with SC in Cycle 1/Period 2 then an optional Cycle 2/Period 2 may still be given but will administered as a cIV infusion instead of SC. If blinatumomab is administered as a cIV infusion it will be dosed at 9 µg/day cIV for 7 days for days 1 through day 7, next the dose will be escalated (dose-step) to 28 µg/day cIV for 7 days starting on day 8 through day 14, and then advanced to 112 µg/day cIV for 28 days starting on day 15 through day 42.

**A treatment-free interval of 14 days will be observed after the completion of the first cycle of blinatumomab before starting the second cycle.**

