**6.2.1.1.3 Optional Cycle 2**

**Optional Cycle 2 for Period 1:** A subject may receive a second cycle of blinatumomab if, in the investigator's opinion, the subject may derive benefit from the treatment. The optional cycle 2 of blinatumomab will be dosed at 9 µg/day cIV for 7 days for days 1 through day 7, next the dose will be escalated (dose-step) to 28 µg/day cIV for 7 days starting on day 8 through day 14, and then advanced to 112 µg/day cIV for 28 days starting on day 15 through day 42. A treatment free interval of 14 days will be observed after the completion of the first cycle of blinatumomab before starting the second cycle.

**Optional Cycle 2 for Period 2:** A subject may receive a second cycle of blinatumomab administered SC if the subject had clinical benefit on scans from treatment given SC in Cycle 1/Period 2 (Section 6.2.1.1.2).

If no clinical benefit on scans after Cycle 1/Period 2, then optional Cycle 2 is administered as a cIV infusion. If cIV is used, blinatumomab will be dosed at 9 µg/day cIV for 7 days for days 1 through day 7, next the dose will be escalated (dose-step) to 28 µg/day cIV for 7 days starting on day 8 through day 14, and then advanced to 112 µg/day cIV for 28 days starting on day 15 through day 42. A treatment free interval of 14 days will be observed after the completion of the first cycle of blinatumomab before starting the second cycle.

Approved

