### **7.3.10 PET-CT Scan and Interim CT Scan**

PET-CT (head to thigh), CT (head/neck, thorax, and pelvic/abdomen), or contrast enhanced CT (head/neck, thorax and pelvic/abdomen as clinically indicated and

evaluated per [Appendix A \[Cheson et al, 2007\]](#) and [Appendix B \[Cheson et al, 2014\]](#)) should be performed within 21 days of the first dose of IP and during the Safety Follow-up visit (2 to 4 weeks after the end of therapy for cycle 1). In the case where a second cycle is administered, the assessment has to be done prior to the start of the next cycle to assess the evolution of disease (as close to 2 weeks after the last dose of IP cycle 1, but before starting cycle 2). Additional PET-CT or CT follow up following the optional second cycle of treatment should be performed during the Safety Follow-up visit (2 to 4 weeks after the end of therapy for cycle 2). The same imaging modality should be used throughout the study for an individual subject.

If PET and CT are acquired on the same day, it is strongly recommended that PET is performed prior to the CT with IV contrast.

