## 8.3 Reasons for Removal From Treatment or Study

### 8.3.1 Reasons for Removal From Treatment

Reasons for removal from protocol-required IP(s) or procedural assessments include any of the following:

- Protocol-specified criteria: a DLT during the DLT evaluation period (see [Section 6.2.1.2.3](#)), neurological event as described in [Section 6.2.1.4.3](#) and [Appendix E](#)
- Subject request
- Safety concern:
  - due to an adverse event
  - pregnancy
  - ineligibility determined
  - protocol deviation
  - non-compliance
  - requirement for alternative therapy (including transplant),
- Death
- Lost to follow-up
- Decision by sponsor (other than subject request or safety concern, lost to follow)
- Disease progression (eg, clinically relevant disease progression, relapse or non-response) **for subjects in Period 1**

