A subject may receive a second cycle of blinatumomab administered SC if the subject derived clinical benefit (demonstrated on staging scans) from Cycle 1/Period 2 treatment. If no clinical benefit occurred with SC in Cycle 1/Period 2 then an optional Cycle 2/Period 2 may still be given but will administered as a cIV infusion instead of SC. If blinatumomab is administered as a cIV infusion it will be dosed at 9 $\mu\text{g/day}$ cIV for 7 days for days 1 through day 7, next the dose will be escalated (dose step) to 28 $\mu\text{g/day}$ cIV for 7 days starting on day 8 through day 14, and then advanced to 112 $\mu\text{g/day}$ cIV for 28 days starting on day 15 through day 42.

Percent Change From Baseline

Percent change from Baseline is the arithmetic difference between post-Baseline and Baseline divided by Baseline values times 100.

Screened

A subject is considered in screening once a consent form has been signed.

Study Day 1

Study day 1 is defined as the first day of administration of the investigational product after enrollment. The day prior to Study Day 1 is considered Day -1.

Study Day

Post study day 1: study day= (date - date of Study Day 1) + 1

Pre study day 1: study day= (date – date of Study Day 1)

Study Duration

For an individual subject, the length of participation includes a 14 day screening period, up to a 14 week treatment period (6 weeks for cycle 1 in Period 1 and Period 2 and 6 weeks for the optional Cycle 2, separated by a 14 day treatment free interval), and a safety follow-up visit (30 days [+ 7 days] after the last dose of study treatment).

For subjects who complete the protocol from the date of first dose through optional Cycle 2, the entire duration of the study will take approximately 20 weeks to complete. However, individual study duration will vary depending on administration of a second cycle and tolerability of blinatumomab by an individual subject.

Treatment emergent adverse events (TEAEs)

A treatment emergent adverse event refers to the adverse event that starts on or after first dose of blinatumomab through 30 days after the last dose of blinatumomab. It is indicated by the flag whether an event start before first dose of blinatumomab on the Event CRF page. This reporting window also applies to treatment-emergent serious adverse events (SAEs).

7. Analysis Subsets

The analysis of all endpoints, unless noted otherwise, will be conducted on the Full Analysis Set defined in [Section 7.1](#).

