7.1 Full Analysis Set

All subjects who receive blinatumomab are included in the full analysis set (FAS). This definition is in line with the intent-to-treat (ITT) principle in single-arm open-label studies. For the dose escalation part of the study subjects will be analyzed according to the initial blinatumomab dose received. For the dose expansion, subjects will be analyzed according to the dose selected for this part of the study.

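### The SAP separates SC from cIV adverse events in Period 1 only, so the Period 2 AE tables pool events from a cIV Cycle 2 with those of the SC expansion

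*SAP*

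**What the plan says.** **Crossover.** Protocol 6.2.1.1.3 states: "If no clinical benefit on scans after Cycle 1/Period 2, then optional Cycle 2 is administered as a cIV infusion". The Protocol Synopsis agrees: "If no clinical benefit occurred with SC in Cycle 1/Period 2 then an optional Cycle 2/Period 2 may still be given", and SAP section 6 repeats the rule. The cIV cycle is a full one: 7 days at 9 µg/day, 7 days at 28 µg/day, then 112 µg/day "cIV for 28 days starting on day 15 through day 42". Subjects with benefit on scans may instead take Cycle 2 by the SC route. Protocol 8.3.1 limits removal from treatment for progression or non-response to Period 1, so a Period 2 non-responder can stay on treatment.

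**Window.** SAP section 6 defines a treatment-emergent event as one that "starts on or after first dose of blinatumomab through 30 days after the last dose of blinatumomab". Neither route nor cycle limits it.

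**Grouping.** SAP 7.1 states: "For the dose expansion, subjects will be analyzed according to the dose selected for this part of the study". SAP 10.5.1 lays the AE tables out by dose cohort.

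**Route split.** The only commitment for adverse events is in SAP 10.5.1: "Tables with AEs as above will be produced for period 1 for SC and cIV dosing separately". Elsewhere the SAP does use route in both periods: exposure (10.5.6) is summarised separately for cIV and SC, and PK parameters (10.7) by dose, period and route.

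**The concern.** The primary objective is the safety and tolerability of SC blinatumomab, and adverse events are half of the primary endpoint. Period 2 is the only part of the trial in which Cycle 1 is given without cIV, and one of its stated aims is additional safety data. Its AE tables are where a reader will look for the profile of the SC regimen.

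No sentence in either document stops the Period 2 AE count at the first cIV dose, assigns later events to cIV, or commits to Period 2 tables by route or cycle. An event that first appears on a cIV infusion, or in the 30 days after it, is then counted in the expansion column headed by the SC dose. The added events come from a selected group, those for whom SC showed no benefit, and their number depends on how many cross over rather than on SC toxicity.

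**Working it through.** **1. The plan's own figure.** Protocol 3.5.1 and SAP section 6 give up to 14 weeks of treatment with Cycle 2: 6 + 2 + 6 = 14. This reproduces.

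**2. Treatment-emergent time per subject**, from those lengths and the 30-day tail:
- SC Cycle 1 only: 42 + 30 = about 72 days.
- SC Cycle 1, then cIV Cycle 2: 42 + 14 + 42 + 30 = about 128 days. Of these, 42 + 30 = 72 days, or 72/128 = 56%, fall on or after the first cIV dose.

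These are calendar days and do not measure events.

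**3. Direction.** The tables count each subject once per term, at worst grade. Adding a second cycle can add a subject to a row or raise a grade; it cannot remove a subject or lower a grade. So the pooled figure is equal to or above the figure for SC alone.

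**4. Size, as a hypothetical.** Let p be the incidence under SC, k the number of 15 who cross to cIV, and q the cIV incidence among those without the event on SC. The documents give none of these.

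Pooled incidence = [15p + k(1 − p)q] / 15

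With p = q = 20%, independent between cycles:

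| k | Subjects counted | Pooled incidence |
|---|---|---|
| 0 | 3.00 | 20% |
| 4 | 3 + 4 × 0.8 × 0.2 = 3.64 | 24% |
| 6 | 3 + 6 × 0.16 = 3.96 | 26% |
| 8 | 3 + 8 × 0.16 = 4.28 | 29% |
| 10 | 3 + 10 × 0.16 = 4.60 | 31% |

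Varying q with p = 20%: for k = 3, q of 10% or 30% gives 21.6% or 24.8%; for k = 10, it gives 25.3% or 36.0%.

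**5. What is not touched.** The MTD is set from Period 1 DLTs. The Period 2 stopping rule counts DLTs, which have their own window (Protocol 6.2.1.2.2, SAP 8.1.1.2). With Cycle 2, the window runs to 16 days after the last Cycle 1 SC dose or to the start of Cycle 2, whichever is longer, capped at 30 days after that dose. The stated total of 56 days implies a last SC dose on day 40 (40 + 16 = 56), one day before the earliest Cycle 2 start (42 + 14 + 1 = day 57). In Protocol Table 6 the q48h and q72h options end on day 42, so 16 days reaches day 58, an overlap of at most two days. That is a detail of the DLT window and does not come from the AE tables.

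**The case against.** The strongest reply is that this is only a matter of table layout. No decision rule uses the tables, no hypothesis is tested (SAP section 5), and the DLRT works from subject-level listings of doses and adverse events (SAP Appendix F). The final report lists every administration (SAP 10.5.6), so nothing is lost. Protocol 10.4.1 allows safety summaries by dose schedule where appropriate, SAP section 11 declares no departure from the protocol, and SAP 7.1 groups subjects without attributing events to a route.

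Most of this stands, and it limits the severity. It does not close the gap. The protocol wording permits a split without committing to one; the SAP's general rule (10.1) names dose cohort and time, not route or cycle; and a separation devised after the data are seen is weaker than one written down now.

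The reply is also right about magnitude. Protocol 2.4 describes cytokine release as transient after treatment starts, so risk in Cycle 2 may be lower than in Cycle 1 and independence between cycles is doubtful. The shift of 0.64 to 1.6 subjects is small against the exact 95% interval for 3 of 15, about 4% to 48%.

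Three stronger readings are tempting, and the documents do not support them:
- **The whole primary endpoint is contaminated.** It is not; the DLT half has its own window and analysis set.
- **Response to SC is contaminated too.** Protocol 7.3.10 does require a later scan: "Additional PET-CT or CT follow up following the optional second cycle of treatment should be performed during the Safety Follow-up visit". But SAP section 6 ties best overall response to the scan at the Cycle 1 follow-up or, if a second cycle is given, to the scan before it starts. The later scan is a procedure outside that definition.
- **AE numerators do not match the route-specific exposure.** Only subject incidence is planned, with subjects as the denominator. Exposure in SAP 10.5.6 is not a denominator for any AE rate.

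**Conclusion.** The point holds for the Period 2 adverse-event tables and no further. Followed as written, the plan counts cIV-onset events in the SC expansion column, and any bias runs against SC. With no crossovers there is no effect. The rise from 20% to about 24% to 31% rests wholly on assumed incidence, independence and crossover numbers; it shows scale and is not a forecast. Because the tables are descriptive and the events can be separated from data already collected, this should be fixed but does not threaten the trial's decisions.

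**What to change.** Replace the route-split sentence in SAP 10.5.1 with a commitment to AE tables by actual route in both periods. For Period 2:

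- **SC table.** Count events with onset from the first SC dose to the earlier of the first cIV dose and 30 days after the last SC dose. The denominator is all treated Period 2 subjects. Keep Cycle 2 SC events in this table and also show them by cycle. Cutting at the start of any Cycle 2 would remove real SC toxicity in subjects who continue on SC.
- **cIV table.** Count events with onset on or after the first cIV dose. The denominator is the subjects who received cIV.

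Use the route actually given, because SAP 8.1.1.2 labels Cycle 2 after Period 2 as cIV while SAP section 6 and the protocol allow either route.

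The cost is SAP wording and one extra set of tables. Route, dose dates and onset dates are already collected, and no sample size or stopping boundary changes. Two small drawbacks should be footnoted: a late SC effect with onset after cIV starts appears in the cIV table, and follow-up after the last SC dose is shorter for crossover subjects (about 14 days, the treatment-free interval, against 30).
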